Hamilton J, 1988 [Esophagitis]	3	3 days	15	No acid exposure time reduction nor clinical improvement	Low power Short follow-up	19
Pollmann H, 1996 [GERD]	NA	2 weeks	NA	No clinical improvement	Full text unavailable Non-structured abstract	21
Khan BA, 2012 [Nocturnal GERD]	1	1 week	20	↓ acid exposure time, clinical improvement	Non-randomized Inpatient setting	18

Table 1: Summary of HBE clinical trials in GERD published to date. NA: Unavailable; PPI: proton pump inhibitor; ↓: reduction

HYPOTHESIS

Head of bed elevation is a useful treatment for patients with GERD and nocturnal symptoms, and has a positive impact in quality of life in these patients.

STUDY OBJECTIVES

General Objective: To assess the effectiveness of HBE for treatment of patients with GERD and nocturnal symptoms, and to determine the impact of this intervention in quality of life of these patients.

Specific Objectives:

- 1. To identify, recruit and randomize participants with strict allocation concealment.
- 2. To compare symptom severity and quality of life among participants allocated to the HBE and the control group, in both the first and second period of study.
- 3. To assess therapeutic adherence and adverse event occurrence periodically by means of telephone call and photographic documentation of patient compliance with assigned intervention.

PATIENTS AND METHODS

General design: Randomized single-blind single-centre controlled clinical trial with a 2x2 cross-over design, in a sample of patients attending to the outpatient visit at the Gastroenterology, Digestive endoscopy and Liver Diseases Unit in Clínica Fundadores, Bogotá city. Participants who meet the inclusion and have no exclusion criteria will be randomized to raise the head of bed with standard 20 cm-height wooden blocks or to sleep without bed inclination during 2 periods of 6 weeks each, separated by a washout 2 week period. During the trial, every patient will receive standard pharmacological treatment with a proton pump inhibitor and/or sodium alginate, according to treating physician criteria, and the researchers in charge of statistical analysis and reporting results will be blinded for the non pharmacological intervention under study. Primary outcome is a significant symptom reduction according to RDQ validated questionnaire and secondary outcomes include quality of life impact according to SF-36 validated questionnaire, patient preference and adverse events of non pharmacological intervention.

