The trial will be conducted during 8 months and will be divided into 4 successive stages.

- 1. Stage I: 2 months during which the first 4 specific objectives will be accomplished.
- 2. Stage II: 4 months for specific objectives 5 to 7.
- 3. Stage III: 1 month for specific objective 8 and results discussion.
- 4. Stage IV: 1 month for specific objectives 9 and 10.

In figure 1 and table 2, different stages with respective component activities are outlined.

[figure not shown]

Figure 1: Clinical trial stages

Patient recruitment: Because of a low recruitment rate, an active participant search system was finally implemented. This system was based on telephone calls, using a database with patient data from all upper gastrointestinal endoscopies performed in the Gastroenterology Unit at Clínica Fundadores in Bogotá city, between years 2014 to 2016. Patients were pre-selected based on endoscopically diagnosed erosive esophagitis of any grade, which is one of the clinical trial inclusion criteria. In order to minimize selection bias, 2 interviewers performed telephone calls in a consecutive chronologic order to all patients in the database without exception. In all cases, the same standardized telephone call format was used.

Sample size: Null hypothesis (H_0) and unidirectional alternative hypothesis (H_1) of the trial are represented below:

$$H_0$$
: RDQ_{HBE}= RDQ_{NoHBE} H_1 : RDQ_{HBE}< RDQ_{NoHBE} H_0 : SF-36_{HBE}= SF-36_{NoHBE} H_1 : SF-36_{HBE}> SF-36_{NoHBE}

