Follow-up: After participant allocation, telephonic follow up will be made during both periods of the trial with a frequency that is dependent on the intervention group of the patient in that period. Participants in the HBE group will be called weekly for 2 weeks, and then will be called biweekly for a month, until each period of 6 weeks has ended. In contrast, patients in the control group will be called every three weeks along each period. With the purpose of verifying both HBE adherence and correct use of wooden prisms, every participant will be asked to send a photograph of the bed head legs during the follow-up telephone call. The photograph will be received by the researcher via e-mail or smartphone and will be encoded and saved in a hard disk. At the end of the first period, RDQ and SF-36 questionnaires will be applied and researchers will store the returned prisms during washout period. When washout period has ended, RDQ and SF-36 questionnaires will be applied again in order to be sure of the absence of any carry-over effect in the group initially allocated to HBE. Finally at week 14, RDQ, SF-36 and Patient Preference questionnaires will be administered to complete study ending outcome assessments.

In figure 5, a schematic representation of follow-up is shown.

[figure not shown]

Figure 5: Schematic representation of photographic and telephonic follow-up. W1-6: Weeks from 1st to 6th in each period.

Primary outcome:

1. Effectiveness: Change of ≥ 0,6 points between basal RDQ questionnaire and the same questionnaire administered after 6 weeks of HBE use.

Secondary outcomes:

- 1. Quality of life: Change of ≥ 10 percentage points between basal SF-36 questionnaire and the same questionnaire administered after 6 weeks of HBE use.
- **2. Patient preference:** Proportion of patients who preferred HBE, after finishing 14 weeks of the study.
- 3. Safety: Proportion of patients with any reported adverse event during HBE or without bed inclination.

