between periods will be transformed into a binomial variable and a McNemar marginal homogeneity test will be applied. McNemar mid-p was used if discordant pairs sum was smaller than 25²⁸. Differences with one-tail p<0,05 will be accepted as statistically significant. Exploratory subgroup analysis will search for differences stratified according to age group, sex, ethnic group, BMI, comorbidities, cups of coffee per day, pharmacological adherence, and length and severity of symptoms; among other 16 baseline variables. Subgroup interactions will be tested with Chi-square or Fisher exact test, and effect size was expressed as a univariate relative risk from a generalized linear model of binomial family. As part of internal quality control of the clinical trial, a pre-test was applied to prove the assumption of a negligible *carry-over* effect, according to expert guidelines²⁹. Analysis of variance (ANOVA) for crossover studies was used in search for significant sequence, period and treatment effects, assuming a negligible *carry-over* effect. In the modified intention to treat analysis, participants with protocol violations because of bad adherence to HBE, were included, but it was not possible to include patients who withdrew from the study because outcome information could not be gathered completely.

Methodology diagram: A schematic representation of the trial methodology is presented in figure 6.

[figure not shown]

Figure 6: Schematic representation of the trial methodology. RDQ: Reflux Disease Questionnaire; SF-36: Short Form 36 Questionnaire; HBE: Head of Bed Elevation; Standard treatment: Based on proton pump inhibitors and/or sodium alginate, according to treating physician criteria.

WORK TEAM

Work team of this clinical trial is formed by three authors. The respective roles during the design and conduction of the trial, and also the professional profiles of each researcher are described below.

Researchers:

- [name] (Principal Researcher study design, patient recruiting, telephonic follow-up, outcome assessment, statistical analysis, writing of final report)
 - General Practice Physician Universidad Nacional de Colombia
 - 3rd year Internal Medicine resident Universidad Nacional de Colombia
- [name](Researcher patient recruiting, intervention administration, clinical and telephonic follow-up, writing of final report)
 - General Practice Physician Universidad Nacional de Colombia

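### Follow-up calls are about twice as frequent in HBE periods as in control periods, so the adverse-event comparison is open to a probably small ascertainment bias against HBE

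*Combined protocol and SAP*

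**What the plan says.** The Follow-up section states that calls are made "with a frequency that is dependent on the intervention group of the patient in that period". For the intervention: "Participants in the HBE group will be called weekly for 2 weeks, and then will be called biweekly for a month", until the 6-week period ends. For the comparator: "patients in the control group will be called every three weeks along each period".

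Specific objective 3 makes these calls a route for collecting harms: "To assess therapeutic adherence and adverse event occurrence periodically by means of telephone call". Secondary outcome 3 (Safety) is the "Proportion of patients with any reported adverse event during HBE or without bed inclination".

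No hypothesis or test is named for safety in particular. The statistical analysis plan does give a general rule that categorical data are compared with a Chi-square or Fisher exact test, and this could be applied to the safety outcome. The visible text gives no adverse-event form, standard question, recall window or allowance for the number of contacts.

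The questionnaires follow a schedule that does not depend on the condition: "At the end of the first period, RDQ and SF-36 questionnaires will be applied". They are applied again after washout and at week 14.

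**The concern.** For adverse events, the telephone call is the stated measuring instrument, and it is used about twice as often in one condition as in the other. An outcome counting patients with any reported event responds to the number of chances to report. If events are forgotten over longer gaps, or if repeated asking prompts reports, HBE periods will show more events even when the true rates are equal.

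The crossover does not balance this out. Each patient passes through both conditions, but the denser schedule moves with HBE, so the imbalance falls on the same side in both sequences. Patients also know when they are using HBE.

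At stake is how the harms comparison is read: HBE could look less well tolerated than it is.

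**Working it through.** The documents state no call total, event rate or recall rate, so there is no planned figure to reproduce. The call counts follow from the text. The size can only be illustrated under assumptions.

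**1. Calls per 6-week period** (Follow-up section; Figure 5 is not visible)

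- HBE, reading biweekly after weekly as every two weeks: weeks 1, 2, 4, 6, so 2 + 4/2 = 4 calls, with gaps of 1, 1, 2, 2 weeks.
- Control: weeks 3 and 6, so 6/3 = 2 calls, with gaps of 3, 3 weeks.

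Both schedules cover the whole 6 weeks. They differ in how long an event waits before someone asks about it.

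**2. Recall model (all assumed)**

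- True proportion with an event: 20% in both conditions; 42 patients.
- At most one brief event per patient, with timing uniform over the 6 weeks.
- A fraction *r* of events is still recalled after each week; *r* = 0.9, 0.7 or 0.5.
- An event is reported only at the next call.

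Fraction captured = (1/6) × Σ over gaps *L* of (1 − *r*^*L*)/(−ln *r*).

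Worked for *r* = 0.7, where −ln *r* = 0.357: the term is 0.841 for a 1-week gap, 1.430 for 2 weeks and 1.842 for 3 weeks.

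- HBE: (2 × 0.841 + 2 × 1.430)/6 = 0.757
- Control: (2 × 1.842)/6 = 0.614
- Spurious excess: 42 × 0.20 × (0.757 − 0.614) = 1.2 patients

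| Weekly recall *r* | Captured, HBE | Captured, control | Reported, HBE v control | Spurious excess of 42 | Ratio |
|---|---|---|---|---|---|
| 1.0 | 1.000 | 1.000 | 20% v 20% | 0 | 1.00 |
| 0.9 | 0.917 | 0.857 | 18.3% v 17.1% | 0.5 | 1.07 |
| 0.7 | 0.757 | 0.614 | 15.1% v 12.3% | 1.2 | 1.23 |
| 0.5 | 0.601 | 0.421 | 12.0% v 8.4% | 1.5 | 1.43 |

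**3. Events that last** (recall decays only once the event has ended; *r* = 0.9, 0.7, 0.5)

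- 1 week: excess 0.4, 1.2 and 1.8 patients
- 2 weeks: 0.1, 0.4 and 0.8 patients
- 3 weeks or more: nil, because every event is still present at the next call

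The excess scales with the assumed event proportion: half at 10%, double at 40%. The model covers forgetting only. Prompting by repeated questions is not modelled, and the documents give nothing from which to size it.

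**The case against.** **The denser calls have a purpose.** The Follow-up section uses the calls to verify adherence and correct use of the prisms. That justifies making them. It does not require the between-condition harms comparison to rest on them.

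**The effect is small.** One remembered event in six weeks is enough for a patient to count, and both schedules run to the end of the period. In a rough check with a one-tailed Fisher test on two independent groups of 42 (pairing ignored), the chance of p < 0.05 for an HBE excess runs from 3.6% to 6.7% over the three recall rates in the table, against 2.7% with no bias. This stands, and it is why the point is minor. It does not remove the effect on a descriptive harms table, where one or two patients are visible.

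**Other collection routes may exist.** The Work team section mentions "clinical and telephonic follow-up", Figures 5 and 6 are not visible, and part of the protocol was not available for review. The data sources listed in the statistical analysis plan include neither a call log nor an adverse-event form, so how events reach the database is unstated. It cannot be said that calls are the only route.

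**Stronger readings that the documents do not support**

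- A reader might take biweekly to mean twice a week, which would make the imbalance much larger. Coming after weekly calls, the word more naturally describes a taper to every two weeks, and Figure 5 may settle the matter.
- A reader might extend the concern to RDQ and SF-36. Both are administered at the same time points in both conditions. Unequal contact is only an unquantified caveat there, and no size is claimed.

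**Conclusion.** The point holds as a minor one. As written, the plan gives about 4 calls per HBE period and about 2 per control period, and it names telephone calls as the means of assessing adverse events. The safety comparison is therefore open to ascertainment bias against HBE, and crossing over does not cancel it.

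The size is unknown and probably small: about 0 to 1.8 spurious patients of 42. That range rests on the assumed 20% event proportion, the assumed weekly recall of 50% to 100%, at most one event per patient, and equal true rates in the two conditions. It is nil with complete recall or with events that persist until the next call.

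A reader might infer that the trial could hide harm from HBE. The bias runs the other way: it can make harms look larger and cannot create a false claim that HBE is safe. It affects one secondary outcome. Confidence is medium, because another collection route or a standard question may lie in material that was not visible.

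**What to change.** **Periods not yet completed.** Ask the same standard adverse-event question on the same call schedule in both conditions. Any additional HBE calls should serve adherence only and should not feed the between-condition comparison. Cost: raising control periods from 2 to 4 calls takes at most (4 − 2) × 42 = 84 extra short calls by the existing callers, and fewer if some periods are complete.

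**Fallback without extra calls.** Keep the current schedule and base the comparison on one identical whole-period question at the end of each period, when the questionnaires are applied anyway. Continue to list all events from every call by condition. The downside is lower capture: under the same recall model (one 6-week gap) the single question captures 74%, 41% and 24% of events at 90%, 70% and 50% weekly recall, against 92%, 76% and 60% with the four HBE calls. Earlier HBE calls may also still prompt recall. The question supports the comparison and does not replace full reporting of harms.

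**Completed periods.** The text describes some conduct in the past tense ("an active participant search system was finally implemented"), so some or all periods may be over. For these, report events and number of contacts by condition, and state that an excess on HBE may partly reflect closer questioning. The only cost is reporting.

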Sample size was estimated based on the hypothesis that HBE would produce a difference of at least 10% in RDQ and SF-36 scores. Effect size (Cohen d) was calculated as 0,49 keeping in mind an RDQ mean and standard deviation of 3,3±1,0 previously found in Spanish population with symptomatic GERD²⁴ and an SF-36 mean and standard deviation of 56,9±20,3 reported in Italian population in medical therapy with PPI²⁵. The minimally important difference selection was chosen based on the assumption that any difference smaller than 10% would have no clinical relevance. Based on this data, 14 patients per group would yield a power greater than 80% for detection of a minimally important difference as large as or larger than 0,6 points in RDQ questionnaire (range: 1 to 6) and 10 points in SF-36 questionnaire (range: 0 to 100), when using a paired t test as described in the statistical analyses plan section. Because of a complementary analysis of crossover data is planned with McNemar marginal homogeneity test, effect size was recalculated based on results of a previous trial²⁰, according to which, 58,8 % and 28,6% of placebo-treated patients in pre-omeprazole era, reported improvement of GERD symptoms with and without a HBE of 20 cm, respectively. Based on these data, and maintaining a statistical power of 80%, required sample size was adjusted to a total of 34 patients. In

figure 2, matrices for sample size calculation are shown, based on the cited trial and using internationally accepted statistical procedures²⁶. Likewise, in table 3 an output of sample size calculation is shown from G*Power 3.1.9.2 (Universität Düsseldorf, Düseldorf, Germany) software²⁷. Finally, calculated sample size was increased by 20% in order to avoid study power loss due to drop-outs or losses of follow-up. Thus, final sample size was 42 patients, 21 per group.

T test	Means: Difference between two dependent means	(matched pairs)
Analysis	A priori: Compute required sample size	
Input	Tails	One
	Effect size dz	0,4926108
	A err prob	0,05
	Power (1- β err prob)	0,8
Output	Noncentrality parameter δ	2,5596808
	Critical t	1,7056179
	Degrees of freedom	26
	Total sample size	27
	Actual power	0,8015888
McNemar	Proportions: Inequality, two dependent groups	
Analysis	A priori: Compute required sample size	
Input	Tails	One
	Odds ratio	3,571
	α	0,05
	1- β	0,8
	Prop discordant pairs	0,53782
Output	Lower critical N	13,0000000
	Upper critical N	13,0000000
	Total sample size	34
	Actual power	0,8169370

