Statistic analysis plan: Quantitative and qualitative variables collected with Basic Data Format, RDQ, SF-36 and Patient Preference questionnaires will be typed in a Microsoft Excel 2007 database. Intervention groups will be masked with an alphabetical code provided by an independent collaborator who will not be involved with data analysis or report writing. For statistical processing, database will be imported into STATA SE 13.0 for Windows (StataCorp LP, Texas, USA) and descriptive statistics will be generated for each variable. Statistically significant differences will be searched for categorical data using the Chi-square test or Fisher exact test and normality will be tested for numerical continuous variables using the Shapiro-Wilk test. For normally distributed continuous variables, statistically significant differences will be searched for by using unpaired Student's t test. Alternatively, for not normally distributed variables Mann-Whitney U test will be applied. For non-normal variables due to atypical data, values outside the percentile 50 ± 1,5 interquartile range were excluded. For complementary processing of primary outcome and secondary outcome quality of life, score difference

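### The RDQ and SF-36 outcomes have no no-HBE comparator and no named main test, and the paired t test behind the power claim is absent from the analysis plan

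*Combined protocol and SAP*

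**What the plan says.** All references are to the combined protocol and SAP.

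- **Objectives and hypotheses.** Specific objective 2 compares symptoms and quality of life between "participants allocated to the HBE and the control group, in both the first and second period of study". The hypotheses under Sample size set the RDQ and SF-36 scores with HBE against those without it.
- **Outcomes.** Under Primary outcome, effectiveness is a "Change of ≥ 0,6 points between basal RDQ questionnaire and the same questionnaire administered after 6 weeks of HBE use". Under Secondary outcomes, quality of life is a "Change of ≥ 10 percentage points between basal SF-36 questionnaire and the same questionnaire administered after 6 weeks of HBE use". Neither has a counterpart for the period without HBE.
- **Sample size.** Power above 80% is claimed "when using a paired t test as described in the statistical analyses plan section".
- **Statistic analysis plan.** For normally distributed continuous variables, "statistically significant differences will be searched for by using unpaired" Student's t test; otherwise, "for not normally distributed variables Mann-Whitney U test will be applied". The passage opening "For complementary processing of primary outcome and secondary outcome quality of life, score difference" makes the between-period score difference binary and applies McNemar's test. A crossover ANOVA for sequence, period and treatment effects follows, with no outcome attached to it.

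**The concern.** Read literally, the primary outcome is an uncontrolled before-after response, which cannot answer the comparative question in the hypotheses. The sample size section points to a test that the analysis section does not contain. The only test tied by name to RDQ and SF-36 is labelled complementary, and no main test is named for it to complement.

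The general rule for continuous variables does not say what the unpaired test is applied to. Three readings fit the text:

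1. HBE against control within each period, which objective 2 permits and which discards the pairing.
2. All HBE scores against all no-HBE scores, treated as independent although each patient contributes to both.
3. Each patient's period difference compared between the two sequences, which is a proper crossover test but is not stated.

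The trial was sized on within-patient information. If the reading is settled only once data exist, the analyst chooses among tests with very different properties. Coded group labels hide which arm is which, but they do not remove that choice.

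**Working it through.** **Inputs.** From Sample size: RDQ difference 0.6 and SD 1.0; SF-36 difference 10 and SD 20.3; 34 patients before the 20% allowance and 42 after. From the analysis plan: one-sided 0.05. The documents give no within-patient correlation ρ, so 0.3, 0.5 and 0.7 are assumed. Power is from the noncentral t distribution, with 34 completers split 17/17 unless stated.

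**Plan's own figures.**
- Paired t: dz = 10/20.3 = 0.4926; noncentrality 0.4926 × √27 = 2.560; critical t 1.706 on 26 df; power 0.8016. N = 27 reproduces, and 14 per group is this rounded up to 28. Using 20.3 as the SD of the differences implies ρ = 0.5, because SD of difference = SD × √(2(1−ρ)).
- McNemar: 0.53782 × 34 ≈ 18 discordant pairs; critical count 13; odds ratio 3.571. Power is 0.8169 and α 0.0481, as in Table 3. The inputs agree with Figure 2. The mid-p version has power 0.810 at 34 and 0.878 at 42.

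The sizing is therefore sound for a paired analysis.

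**Reading 1: unpaired within one period.** Noncentrality = (difference/SD) × √(n/2), with n per group and 2n−2 df.
- RDQ: 0.6 × √8.5 = 1.749 against critical t 1.694; power 0.527. With 21 per group, 0.605. For 80%, 36 per group.
- SF-36: 0.4926 × √8.5 = 1.436; power 0.406. With 21 per group, 0.470. For 80%, 52 per group.

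**Reading 2: 34 HBE scores against 34 no-HBE scores.** The test assumes the variance of the mean difference is 2·SD²/34. The true variance is 2·SD²(1−ρ)/34, so the standard error is too large whenever ρ > 0. By simulation (100,000 runs), for RDQ:

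| ρ | Type I error (nominal 0.05) | Power |
|---|---|---|
| 0.3 | 0.026 | 0.830 |
| 0.5 | 0.011 | 0.869 |
| 0.7 | 0.002 | 0.921 |

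**Reading 3: crossover treatment term.** SE = 0.5 × SD × √(2(1−ρ)) × √(1/17 + 1/17), 32 df. For RDQ at ρ = 0.5, SE = 0.5 × 1 × 1 × 0.343 = 0.1715 and noncentrality is 0.6/0.1715 = 3.50.

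| ρ | RDQ power, N = 34 | SF-36 power, N = 34 | SF-36 power, N = 42 |
|---|---|---|---|
| 0.3 | 0.894 | 0.768 | 0.843 |
| 0.5 | 0.962 | 0.878 | 0.932 |
| 0.7 | 0.997 | 0.976 | 0.992 |

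At ρ = 0.3, SF-36 needs 38 completers for 80%. An unpaired t test on each patient's period difference between sequences is the same test as this term; on simulated data both gave t = −2.012 on 32 df.

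**ANOVA or plain paired t.** Simulated with no HBE effect, a period drift of 0, 0.3 or 0.6 RDQ points, and 34 completers split equally or unequally between sequences (drift and splits assumed):

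| Test and split | Type I error |
|---|---|
| ANOVA, 17/17, 13/21 and 21/13 | 0.049–0.051 |
| Paired t, 17/17, drift 0 / 0.3 / 0.6 | 0.049–0.050 / 0.039–0.044 / 0.018–0.032 |
| Paired t, 13/21, drift 0.3 / 0.6 | 0.091–0.110 / 0.126–0.153 |
| Paired t, 21/13, drift 0.3 and 0.6 | 0.001–0.021 |

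The paired t does not adjust for period, so its error moves either way when completers are unbalanced. McNemar shares the weakness: with a week-0 baseline for both conditions it gives 0.030–0.044 at 17/17, and 0.070–0.082 at 13/21 with drift 0.3.

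**The case against.** The strongest reply is that the gap is one of labelling. RDQ and SF-36 are the only outcomes measured at the end of each period, so the crossover ANOVA can hardly refer to anything else. The hypotheses and Figure 2 already state the contrast with no HBE, and the unpaired rule may be meant for baseline data. This stands in part: the right test is in the plan and the comparator appears elsewhere. But nothing designates that test as the main one, and the sample size text points to a different test that is absent.

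Second, only reading 1 costs RDQ its power. Reading 2 is conservative and keeps RDQ power above 0.80. That is correct, so the pooled reading carries no false-positive risk under these assumptions. It still does not run at its stated error rate, and it has less power than the crossover term.

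Third, the smallest repair would be to add the paired t test. At 17/17 its error never exceeds 0.05, and the inflation at 13/21 rests on an assumed drift and split; with the split reversed the error falls. That is fair. But withdrawals are left out of the modified intention-to-treat analysis, so unequal completers are plausible, and the ANOVA is already planned.

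Fourth, the meaning of "basal" is open, since questionnaires are also given after washout. The follow-up section gives carry-over checking as the purpose of that visit, which supports week 0, but the plan should say so.

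**Conclusion.** The concern holds. The power statement relies on a test that the analysis section does not contain, the RDQ and SF-36 outcomes omit the comparator in the hypotheses, and no main test is named. For RDQ with 34 completers, the readings that fit the text range from power 0.53 to 0.89–0.997, and one has a true error of 0.002–0.026 in place of 0.05. These figures rest on the plan's SDs and differences, one-sided 0.05, and assumed correlations of 0.3 to 0.7. The contradiction between the two sections does not depend on any assumption. The sample size calculations themselves reproduce. The defect should be fixed but does not threaten the design, because the scheduled data support the correct analysis. Figures 5 and 6 were not available and nothing here relies on them.

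**What to change.** - State the main RDQ analysis as the within-patient difference, end of HBE period minus end of no-HBE period. Test it by the treatment term of the crossover ANOVA already planned, and report the estimate with its confidence interval. Do the same for SF-36.
- Restrict the unpaired t test and Mann-Whitney to baseline comparisons between sequence groups.
- Correct the sample size section to refer to this within-patient test.
- For McNemar, define response (RDQ reduction of at least 0.6; SF-36 increase of at least 10) separately with and without HBE. Measure both from the week-0 questionnaire and cross-tabulate per patient as in Figure 2. Keep McNemar complementary, because it does not adjust for period.
- For SF-36, state the power at N = 34: 0.88 at ρ = 0.5 (implied by the plan's effect size) and 0.77 at ρ = 0.3, or 0.84 with 42 completers.
- Parts of the analysis section are in the past tense. If any comparative analysis had been done before the main test was named, say so.

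The cost is wording in the outcomes, sample size and analysis sections. Questionnaires at weeks 0, 6, 8 and 14 are already scheduled. N = 34, inflated to 42, is unchanged for RDQ and McNemar. For SF-36 at ρ = 0.3, power falls below 80% if fewer than 38 patients complete.
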